CLINICAL STUDY PROTOCOL

Interventional Drug or Biologic

Examining the Effect of Varying Water Content of E-liquids on Sensory Experience

Protocol Number

2000031495

NCT05257109

Protocol Version

5-25-22

Version # 3

PRINCIPAL INVESTIGATOR:

Name: [name]

Department: Psychiatry

[contact]

Email Address: [contact]

IND Number:

IND Holder:

NCT Number: N/A

Study Phase (1, 2, 3, or 4-postmarketing):

Confidentiality Statement:

REVISION HISTORY:

Revision #	Version Date
3	5-25-22

Synopsis

Primary Objective

The primary objective of this study is to examine whether (a) sensory irritation and (b) appeal are decreased in e-liquids containing flavor aldehydes (i.e. vanilla, cherry, cinnamon) compared to e-liquids not containing flavor aldehydes (i.e. grape) when the water concentration is increased from the baseline water concentration to the following levels; 5% total water volume, 10% total water volume, 20% total water volume.

Secondary Objective (if applicable)

At each water concentration, we will examine if there are differences in perception of sensory irritation and appeal across the distinct aldehyde containing flavors.

Study Duration

2 years to complete study from HIC submission; we anticipate the subject enrollment period will be 8 months (approximately 1 week/participant). Enrollment began in August 2022, so anticipated subject enrollment will end in March 2023.

Study Design

Within subjects' human laboratory experiment

Number of Study Sites

1; Yale School of Medicine. Yale sites include Connecticut Mental Health Center (intake visits) and John B. Pierce Laboratory (lab sessions).

Study Population

Population is regular e-cigarette users who report use of both nicotine and flavors in their e-cigarettes. We are assessing response to alterations of water level in e-cigarettes among regular users as a potential regulatory tool, so current participants must have regular nicotine experience.

Number of Participants

30; pilot study

Primary Outcome Variables

- (1) Change in irritation at each water level as measured by the Generalized Labeled Magnitude Scale (gLMS)
- (2) Change in appeal at each water level as measured by the Labeled Hedonic Scale (LHS), Drug Effects Questionnaire (DEQ)

Secondary and Exploratory Outcome Variables (if applicable)

1.1 Introductory Statement

This document is a protocol for a human research study. The purpose of this protocol is to ensure that this study is to be conducted according to ICH GCP guidelines, and according to CFR 21 Part 312, other applicable government regulations and Institutional research policies and procedures.

2 Background

2.1.1 Preclinical Experience

See background (2.2) for all relevant information.

2.1.2 Clinical Experience

See background (2.2) for all relevant information.

2.2 Background/prevalence of research topic

Most US tobacco products contain a wide variety of flavorants, with an estimated 15000+ flavors in e-cigarettes (e-cigs) alone.¹ Flavors may enhance the appeal of tobacco products by their positive attributes (e.g. aroma/taste of sweet flavors) and/or by their ability to ameliorate nicotine/tobacco harshness (e.g. cool flavors)¹⁻⁴.

While the Family Tobacco Prevention and Tobacco Control Act (FSPTCA) banned the sale of cigarettes with added artificial and natural flavors in 2009, flavors are currently produced and available in electronic cigarette products. Even new FSPTCA regulations (introduced in May 2016) do not include any of the other assortments of flavors or sweeteners in any of the other tobacco products (e.g., e-cigs). One potential reason for the limited action on flavors is the limited scientific evidence on the influence on flavors and sweeteners on nicotine's abuse potential. To support the regulation of tobacco products, the FDA requires rigorous scientific information on which to base their rulings and support these rulings in legal challenges. These regulatory decisions are further complicated by the multitude of flavors available in tobacco products and the constant innovation by the tobacco industry to use flavorant chemicals to enhance and maintain appeal for these products.

As flavors continue to be available in these products and used by e-cigarette users, one aim of researchers is to develop ways to reduce potential toxicity of these products. Flavor chemicals in e-liquids may expose users to respiratory harms.^{2,3} While many flavor chemicals used in e-liquids are designated as GRAS (generally recognized as safe), this designation applies to oral ingestion, not inhalation.⁴ Levels of flavor chemicals in e-cigarettes vary widely, with flavors accounting for as much as 34% of the e-liquid.⁵ Currently, there are no regulations to mitigate risk associated with flavor chemicals in e-cigarettes.

E-cigarettes contain many different ingredients to produce flavors. A common class of e-liquid flavor chemicals are called aldehydes. Aldehyde flavor constituents are used in many popular flavors.^{5,6} For example vanillin produces a vanilla flavor and is added to many sweet and dessert e-liquids, benzaldehyde produces the popular fruit cherry flavor and is used in many fruit/sweet e-liquids, and cinnamaldehyde produces a cinnamon flavor, which is added to dessert flavored e-liquids, spice flavored e-liquids, and fruit e-liquids (e.g. cinnamon apple).

Aldehydes are sensory and respiratory irritants and activate the sensory receptor TRPA1, an ion channel known to contribute to inflammation and cytotoxicity in airway tissue.^{7,8}

Aldehydes can undergo chemical reactions with the solvents that form the base on e-liquids; propylene glycol (PG) and vegetable glycerin (VG) to form chemical adducts named *flavor*

aldehyde PG/VG acetals (referred to as acetals henceforth). Recent studies have shown that acetals form under typical storage conditions⁹, are present in several commercial e-liquids including popular JUUL products,^{3,9-11} and can efficiently transfer to e-cigarette aerosols.⁹ Acetals have been shown to cause both greater sensory irritation and cytotoxicity at the sensory receptor TRPA1 than their parent aldehydes in-vitro, suggesting that this chemical conversion can have negative health implications for users.^{3,9} **One way to measure user experience of irritant effects would be to have users' rate associated sensory irritation experienced.**

Preliminary (unpublished) evidence from our chemistry lab at the Yale Tobacco Center of Regulatory Science (TCORS) have indicated that it may be possible to reduce acetal formation simply by adding water to e-liquids. This reduces acetal formation by shifting the chemical equilibrium of the formation reaction. Water is physiologically innocuous to inhale via e-cigarette and adding water to e-liquids may be an elegant way to reduce the sensory irritation and cytotoxicity of e-liquids that contain flavor aldehydes. However, adding water also inherently dilutes the flavor and nicotine concentration of the product, which may reduce the appeal overall. This could be a negative outcome if trying to use flavors as a tool to shift combustible cigarette users to potential reduced harm e-cigarettes. However, if irritation is reduced and appeal is not significantly reduced, a regulation requiring a fixed level of water to e-liquids could be a simple and effective tool to reduce potential toxicity in e-liquids with these flavors. *The goal of the proposed study is therefore to determine if the sensory irritation (a marker of potential toxicity) of commercial e-liquids, can be reduced by increasing their water content without adversely affecting flavor appeal in adult e-cigarette users.*

3 Rationale/Significance

3.1 Problem Statement

Electronic cigarettes (e-cigarettes), once considered an emerging tobacco product, are now the most commonly used tobacco product among youth and growing in popularity among adults.^{12,13} Some data suggests that shifting combustible cigarette users to e-cigarette use may have a net positive population benefit.¹⁴ An important facet of e-cigarette appeal is the availability of flavors,^{15,16} including non-tobacco flavors like fruit, dessert, candy, and mint.¹⁷ Non-tobacco flavors may be important for encouraging product switching among combustible tobacco users.^{18,19} However, flavor chemicals in e-liquids may expose users to respiratory harms.^{2,3} While many flavor chemicals used in e-liquids are designated as GRAS (generally recognized as safe), this designation applies to oral ingestion, not inhalation.⁴ Levels of flavor chemicals in e-cigarettes vary widely, with flavors accounting for as much as 34% of the e-liquid.⁵ Currently, there are no regulations to mitigate risk associated with flavor chemicals in e-cigarettes.

A common class of e-liquid flavor chemicals are aldehydes (e.g. vanillin producing a vanilla flavor; benzaldehyde producing cherry flavor; cinnamaldehyde producing cinnamon flavor).^{5,6} Aldehydes are sensory and respiratory irritants and activate the sensory receptor TRPA1, an ion channel known to contribute to inflammation and cytotoxicity in airway tissue.^{7,8} Aldehydes can undergo chemical reactions with the e-liquid solvents propylene glycol (PG) and vegetable glycerin (VG) to form chemical adducts named *flavor aldehyde PG/VG acetals* (referred to as acetals henceforth). Recent studies have shown that acetals form under typical storage conditions⁹, are present in several commercial e-liquids including popular JUUL products^{3,9-11} and can efficiently transfer to e-cigarette aerosols.⁹ Acetals have been shown to cause both greater sensory irritation and cytotoxicity at the sensory receptor TRPA1 than their parent aldehydes in-vitro, suggesting that this chemical conversion can have negative health implications for users.^{3,9}

This study is based on preliminary evidence from our lab that adding water to e-liquids containing flavor aldehydes reduces acetal formation by shifting the chemical equilibrium of the formation reaction. Reducing acetal formation through the addition of physiologically innocuous water may be an elegant way to reduce the sensory irritation and cytotoxicity of e-liquids that contain flavor aldehydes. However, it is possible that adding water might negatively impact the potential value of these flavors for switching from combustible cigarettes by diluting flavorant and nicotine concentrations", potentially resulting in lower delivery per puff. *The goal of the proposed study is therefore to determine if the sensory irritation (a marker of potential toxicity) of commercial e-liquids, can be reduced by increasing their water content without adversely affecting flavor appeal in adult e-cigarette users.*

3.2 Purpose of Study/Potential Impact

The goal of the proposed study is to determine if the sensory irritation (a marker of potential toxicity) of commercial e-liquids containing aldehydes compared to a control non-aldehyde

containing e-liquid, can be reduced by increasing their water content without adversely affecting flavor appeal in adult e-cigarette users. Given that adding water to e-liquid is an innocuous manipulation, if irritation is reduced and effect on appeal is limited, this could be a tool for regulation to reduce harm associated with e-cigarettes.

3.2.1 Potential Risks

Participation in this study is thought to involve a minor increase over minimal risk. Potential risks and protections against risks are detailed below.

(1) E-cigarette Exposure: All participants will be required to have current regular experience with nicotine containing flavored e-cigarettes. Given this, the likelihood of adverse experience with study e-cigarettes/e-liquids is low. Additionally, we will only expose participants to two puffs per flavor x water level manipulation for a total of 32 puffs (16 puffs/lab session) across the study. Participation is voluntary and participants can stop anytime they want and/or if they experience adverse events from nicotine or flavor exposure.

There have been reported cases of severe pulmonary illness linked to vaping or e-cigarette use (i.e. E-Cigarette or Vaping Associated Lung Injury; EVALI). These cases were first reported in August 2019. These cases included symptoms such as cough, shortness of breath, chest pain, nausea, vomiting, stomach pain, diarrhea, fever, chills, or weight loss. Some patients reported symptoms to have occurred over a few days and some reported to have occurred over a few weeks. Vaping-related disorders have ranged from mild to severe with hospitalization, intensive care with breathing machines and in some cases death. In most cases, but not all, people experiencing these symptoms were using cannabidiol (CBD) and marijuana (THC) e-liquids, and/or using e-cigarette devices and e-liquids that were mixed at home or purchased off market (such as purchasing an e-liquid or device on the street, not from a licensed retailer).

Laboratory data shows that Vitamin E Acetate, an additive in some THC-containing e-cigarette or vaping products, is strongly linked to EVALI.

Products used in our study are purchased only from a licensed retailer and do not contain CBD, THC, or Vitamin E Acetate, so the risks of developing EVALI as a result of study participation are highly unlikely. However, we will monitor for EVALI symptoms at intake and at each lab session using an assessment checklist developed in response to EVALI by our lab, the health assessment checklist (included in study measures). Any study participant reporting current THC/CBD vaping and report of mild or greater EVALI-related symptoms (i.e. cough, shortness of breath, chest pain, nausea, vomiting, stomach pain, diarrhea, fever, chills, or weight loss) without non-EVALI reasonable and proximal cause will be ineligible or withdrawn and recommended.

Additionally, e-cigarette liquids contain propylene glycol and vegetable glycerin, which some people may be allergic to. As participants are current e-cigarette users', so all participants will have prior exposure to these constituents. Additionally, we will only allow participants with experience with flavored e-liquids. We will confirm at intake they do not have known allergies to either of these products or e-liquid flavors.

(2) E-Liquid Water Manipulation: Some of the e-liquids participants will use will have water added to liquid at levels, so total water level of the e-liquid is 5% total volume, 10% of total volume, 20% total volume. Unmanipulated e-liquids contain some level of water. There is no evidence that the addition of water will produce any additional harm to e-cigarette users or that e-cigarette device will heat water to a level that produces harm.²⁰ Evidence suggests that addition of water may reduce irritation associated with e-cigarette use.

(3) Nicotine Exposure: E-liquids will contain moderate levels of nicotine salts (36mg/ml). Common side effects of nicotine include nausea, vomiting, heartburn, and elevated heart rate and blood pressure. Toxic doses of nicotine may cause abdominal pain, hypersalivation, diarrhea, dizziness, confusion, hearing and vision problems, syncope, seizures, hypotension, irregular pulse, and death. However, these toxic effects occur at doses 40 to 50 times higher than those that will be used in our studies. Moreover, by recruiting adults who already have experience with e-cigarettes and nicotine, we will further mitigate the risk of these side effects.

(4) Flavor Exposure: We will expose participants to four different e-liquids flavors; cinnamon, cherry, vanilla, and grape e-liquid. All e-liquids are commercially available currently, except for the cinnamon e-liquid, which is currently only available for research use. This cinnamon e-liquid was developed to mirror commercially available cinnamon products. Cinnamon flavoring is known to have health impacts at levels much higher than participants will be exposed to in this study.²¹ We are not aware of any effects from the other flavors being used in this study but participants will be told that if they feel any adverse events or want to stop they are free to do so. Additionally, we will exclude anyone that reports allergies to any of the four flavors used. In the consent form, we will not state the flavors being used, but will note that one flavor is not currently commercially available.

(5) Urine/Saliva Collection: Urine/saliva collection at intake and during the study for females and should add no risks other than those normally associated with these procedures.

(6) Rating Scales and Assessments: These are all noninvasive and should add no risk. The major disadvantages are the time taken to complete them, and possible breach of confidentiality. Our past experience with these measures indicates that they are acceptable to subjects.

(7) Limits to confidentiality: All participants will be specifically told that we will not reveal any personal information collected as part of the research procedures, including their reported use of e-cigarettes and other substance use history. However, there is always the possibility that participation in this study may make others, such as friends and family members, aware of their tobacco use status. They will be told that if they do not feel comfortable with this, then they should not participate in the project. They will also be told that if they report any information to us about abuse or homicidal/suicidal behavior, we will be required to report this information to the appropriate authorities.

Protections Against Risk: We will reduce risks by:

- Requiring participants to be regular nicotine & flavor e-cigarette users.
- Administering briefest possible exposure needed for our outcomes to each study product (2 e-cigarette puffs/product)
- Using well-defined inclusion/exclusion criteria to rule out participants with pre-existing medical conditions
- Providing participants with written information on reducing e-cigarette use at the end of study participation.
- Using study staff who have expertise conducting tobacco research and working with adults and who are sensitive to the issues that may arise in working with e-cigarette users.
- Protect right to privacy through coding of data and proper storage of research records.
- Obtain a certificate of confidentiality from NIH to further protect the research records of these participants.

- Use the Yale TCORS Independent Data Safety Monitoring Board including experts in the field of tobacco use behaviors and challenge studies ([name], FRCPC, Professor and Co-Director, Division of Brain and Therapeutics, Dept. of Psychiatry, U of Toronto; [name], Professor and Chair, Department of Health Outcomes & Behavior, H. Lee Moffitt Cancer Center & Research Institute) and a statistical expert ([name], Assistant Professor of Neurobiology, Columbia University) .

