E-liquid Administration/Participant Instructions/Pausing due to AEs: Participants will be administered e-liquid in an observed laboratory setting in which they are instructed to take two directed puffs of each e-liquid at each water concentration. Between 2-puff puff bouts, participants will be required to wait 10-minutes before engaging in next puff bout. Participants are not allowed to leave the site with product. There will no changes in nicotine concentration (only flavor administered) and all participants will sample all flavor/water concentration manipulations. The lab sessions will be conducted by trained research staff who are sensitive to the adolescent and smoking population and trained to monitor any potential adverse effects. Heart rate, blood pressure, and pulse oximetry will be assessed at baseline and every in-person visit for safety. If they experience any side effects or concerns during the study, we ask them to let us know. Participants will be told that they are able to stop the study at any point. If they feel any discomfort or need to stop for any reason, they can let the research team know. In the event of a serious adverse event, the PI ([name]), will consult with Yale Tobacco Center for Regulatory Science (TCORS; the funder of

this pilot) co-Is, [name] [name] and [name], along with center chemosensory expert [name] to determine if blind needs to be broken. Given all study participants are administered all e-liquids, the study will be paused during this period.

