acute responses to the e-cig on a 0 to 100 mm scale, from “not at all” to “extremely.” Following each 10-puff bout, we will assess E-cig Liking/Wanting (average of “I feel good e-cig effects”, “I want more of that e-cig I received”, “I feel the e-cig strength” and “I like the e-cig effect”). At baseline and following each fixed-dose bout, we will also assess Stimulant effects (average of “I feel energized” and “I feel high”), and Nicotine Withdrawal (average of “I feel sleepy”, “I feel angry”, “I feel irritable”, “I am having difficulty concentrating”, “I feel restless” and “I feel hungry”). **E-cig Effects will be used to assess change in overall appeal (primary outcome).**

4. Multiple Choice Questionnaire to assess e-cig value (Adapted from Multiple Choice Procedure (MCP))^{25,26}: At the end of each 2-puff puff bout, participants will be asked to make discrete hypothetical choices between 10-puffs of the e-cig they had just used or a series of 44 monetary values (\$0.25-\$15.06). The minimum monetary value at which money is chosen over the e-cig puffs is a contingency-based estimate of e-cig value. At the end of each lab session, participants will be given a choice between another 10 e-cig puffs or one of the monetary amounts they picked in the MCPs completed earlier. **MCP will be used to assess change in overall appeal (primary outcome).**

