completion of baseline assessments, at Lab 1, participants will be familiarized with the sensory and hedonic scales and trained in how to puff the e-cigarette (using non-nicotine and non-flavored e-liquid). Participants will then begin testing procedures for their assigned Flavor 1, which will be administered under double-blinded randomized conditions (see above). For each flavor, participants will take two puffs of the flavor when diluted by four levels of water concentration. Participants will be instructed to take two 3-second puffs with a 30 second inter puff interval. Each two-puff bout will be separated by 10-minutes. These procedures are adapted from our recent work (HIC #2000023077), with the number of puffs is reduced as we are not examining the effects of nicotine and only sensory effects of flavor. Per our current practice we will record timed instructions for each puff bout and participants will be trained to follow these directions. Following each puff exposure participants will complete the General Labeled Magnitude Scale (gLMS) for measures of overall intensity, irritation, coolness and sweetness, the Labeled Hedonic Scale (LHS) for measures of liking, the E-Cig Effects Questionnaire for measures of e-cigarette drug effects, and the Multiple-Choice Questionnaire to assess e-cigarette value. Participants will complete the above procedures for two flavors and four water concentrations for each flavor during each lab session. For each flavor, water concentration order will not be randomized and will be presented from hypothesize least irritating (20% water concentration) to hypothesized least irritation (e-liquid as commercially available with no water dilution) to a) maintain consistency of presentation of water concentration across flavors and b) to avoid potential irritation effects from hypothesized more irritating products to less irritating products. Following at least 24 hours, participants will repeat procedures with the remaining two flavors. Each lab session will last approximately two hours.

Debrief

At the end of Lab 2, participants will be thanked for their participation and ask to evaluate the four flavors they sampled (i.e. guess what flavors they tried, what nicotine concentration they e-liquids were) and will be given information from the CDC on e-cigarette cessation.

Table 1. List of Study Assessments

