7.1 Ethical Considerations: Informed Consent/Accent and HIPAA Authorization

The study will be conducted in accordance with the conducted in accordance with the ethical principles that have their origin in the Declaration of Helsinki.

Participants will not be told of the flavors administered, the water concentration administer, or the nicotine concentration of the product. They will be told that products containing moderate levels of nicotine, flavorings that do or do not contain components considered "flavor aldehydes" and that we will be adding water to some of the formulations they will be trying. We will inform participants of this in the consent and indicate that we do not plan to tell them as we do not want prior perceptions of nicotine content or flavors to influence their experience with the product. Participants will be asked not to sign consent if they are uncomfortable with this.

Participants will be compensated \$50 for completing both parts of intake (\$30 for remote portion, \$20 for in person portion). This is commensurate to other e-cigarette studies in our labs. Participants will be compensated \$75 for each laboratory session that is approximately 2 hours in length. Additionally, participants are asked to abstain from vaping for 2 hours prior to each lab session, so this compensation is included. Additionally, at in person appointments, participants will be compensated for travel with \$25. This is the equivalent of the cost of a rideshare in the greater New Haven area to and from our appointment space. Given the short duration of the study and participant preference in previous vaping studies, all compensation will be provided in cash.

The only potential unknown condition identified by the study team that could be discovered as a result of study procedures would be EVALI, due to increased health monitoring for EVALI symptoms. This is included as an added study benefit. During the study, they will be monitored for EVALI related symptoms. Any endorsement of EVALI symptoms that does not have a clear related and proximal cause will result in withdrawal and participants will be referred to a primary care provider.

No information from this study will be added to participant medical records.

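### The stated total of 32 puffs (16 per session) omits the 10 further puffs offered at the end of each session; if that offer is real, the total is 32, 42 or 52, with up to 26 in a session.

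*Combined protocol and SAP*

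**What the plan says.** Section 3.2.1, item (1), limits exposure to two puffs per flavor and water level, "for a total of 32 puffs (16 puffs/lab session) across the study". The list of protections at the end of that section includes "Administering briefest possible exposure needed for our outcomes to each study product (2 e-cigarette puffs/product". The E-liquid Administration paragraph in Section 6.1 agrees: participants are "instructed to take two directed puffs of each e-liquid at each water concentration". So does Section 6.3, Lab Visits: "Participants will complete the above procedures for two flavors and four water concentrations for each flavor during each lab session".

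Section 6.2.1, item 4 (Multiple Choice Questionnaire), describes two kinds of choice. After each two-puff bout, participants choose between 10 puffs and a series of money values from $0.25 to $15.06; these choices are called hypothetical. Then: "At the end of each lab session, participants will be given a choice between another 10 e-cig puffs or one of the monetary amounts", the amounts being those selected after the bouts. This second choice is not called hypothetical.

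The Administration paragraph also states: "Participants are not allowed to leave the site with product". Any puffs chosen would therefore be taken at the site.

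**The concern.** The risk section gives a total for the whole study, not a subtotal for the rating bouts, and the efficacy section describes further puffs that would come on top of it. The offer is absent from the risk text, the administration text, the lab procedures and Table 1. The compensation text in Section 7.1 lists payments for intake, sessions and travel, says "all compensation will be provided in cash", and does not mention the money alternative.

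What is at stake is the accuracy of an exposure figure used to justify low risk. Other statements also lean on brief exposure: Section 6.3.6 gives it as a reason for no follow-up, and Section 7.12 uses it in the monitoring rationale. Section 6.1.1 reports that the FDA had no concerns about use as the protocol describes it, and that same section describes two directed puffs of each liquid. If the offer is delivered, anyone who chooses puffs exceeds the exposure on which these statements rest.

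**Working it through.** **Inputs**

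- Flavors: 4; water levels: 4 (Sections 5.1 and 6.1.4)
- Puffs per flavor and water level: 2 (Section 3.2.1)
- Lab sessions: 2, with 2 flavors at 4 water levels in each (Section 5.1)
- End-of-session offer: 10 puffs or money, once per session (Section 6.2.1, item 4)

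**Reproducing the stated figures**

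- Total = flavors x levels x puffs = 4 x 4 x 2 = 32
- Per session = 2 x 4 x 2 = 16, and 2 x 16 = 32

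Both figures reproduce exactly, so the multiplication is not in dispute.

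**Adding the offer**

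Let k be the number of sessions in which puffs are chosen. Total = 32 + 10k; increase = 10k / 32.

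| k | Total puffs | Increase over 32 |
|---|---|---|
| 0 | 32 | 0% |
| 1 | 42 | 10/32 = 31.25% |
| 2 | 52 | 20/32 = 62.5% |

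The session maximum is 16 + 10 = 26, an increase of 10/16 = 62.5%. For someone who completes both sessions, 32 is then the minimum.

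**Per product**

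The liquid used for the extra puffs is not stated. Assume that all 10 are of one liquid tested in that session, and read product as one flavor at one water level. That product then reaches 2 + 10 = 12 puffs, against the 2 listed as a protection.

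**What these counts leave out**

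Practice puffs at Lab 1 use liquid without nicotine or flavor, and their number is not given. The figures above count study liquids only, assuming the offered puffs are of a study liquid.

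**A separate wording conflict**

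Section 6.2.1, item 3, times the liking and wanting items after 10-puff bouts. Everywhere else the bouts are two puffs, and Section 6.3 and Table 1 place the questionnaire after every administration. Taken literally, 10-puff bouts would give 16 x 10 = 160 puffs, or 80 per session. This is not included in the 42 and 52.

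**The case against.** The best counter-argument is that Section 6.2.1 may carry text from another design. Item 3 refers to 10-puff and fixed-dose bouts that fit nothing else here, and Section 6.3 says the procedures were adapted from earlier work with fewer puffs. The choices after each bout are hypothetical, and the sections that would have to implement the offer do not mention it. On this reading 32 is right and the sentence in item 4 is the error.

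That possibility stands, and it is why 42 and 52 are conditional. It does not remove the contradiction: the sentence says participants will be given the choice, in each session, without the qualifier applied to the earlier choices. If the offer is not delivered, that sentence needs correcting.

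It is also fair that the extra puffs would be elective, that participants are regular nicotine e-cigarette users who may stop at any time, and that the offer follows all of a session's ratings. The 12-per-product figure rests on several assumptions and is only illustrative.

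The nicotine margin in Section 3.2.1, item (3), "these toxic effects occur at doses 40 to 50 times higher than those that will be used in our studies", adds little. Its basis (bout, session or study) is not given, so no revised margin can be computed, and that gap exists with or without the offer. Finally, Figure 1 and the consent pages were not available and may already cover the step.

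**Conclusion.** The concern holds. As written, the plan gives 32 puffs as the study total and elsewhere allows up to 52, and gives 16 per session while allowing up to 26. The excess over the stated total is 0%, 31.25% or 62.5%, according to how often puffs are chosen. The contradiction between Sections 3.2.1 and 6.2.1 is certain. Actual exposure above 32 depends on the offer being delivered, which the documents leave open. This is an internal inconsistency in a safety-relevant figure, not a multiplication error, and it does not touch the outcome analyses. It should be corrected.

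**What to change.** State in Section 6.2.1, item 4, whether the end-of-session choice is delivered.

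- **If it is delivered:** give the resulting maximum per session and in total in Section 3.2.1 and wherever else exposure is described; reconcile the per-product protection with it; say which liquid is used; and add the step to Section 6.3, Table 1 and the compensation text in Section 7.1. Check that the consent material matches.
- **If it is not delivered:** correct item 4 so that it agrees with the stated total.

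Separately, reconcile the bout size in Section 6.2.1, item 3, with the Administration paragraph, Section 6.3 and Table 1.

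The cost is protocol wording, plus consent wording only if it does not already match. The main test procedures do not change. Which exposure is intended is for the study team to state.
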